## **9. STUDY DOCUMENTATION, MONITORING, AND ADMINISTRATION**

### **9.1 STUDY DOCUMENTATION**

The investigator must maintain adequate and accurate records to enable the conduct of the study to be fully documented, including but not limited to the protocol, protocol amendments, Informed Consent Forms, and documentation of IRB/EC and governmental approval. In addition, at the end of the study, the investigator will receive the patient data, including an audit trail containing a complete record of all changes to data.

### **9.2 PROTOCOL DEVIATIONS**

The investigator should document and explain any protocol deviations. The investigator should promptly report any deviations that might have an impact on patient safety and data integrity to the Sponsor and to the IRB/EC in accordance with established IRB/EC policies and procedures. *The Sponsor will review all protocol deviations and assess whether any represent a serious breach of Good Clinical Practice guidelines and require reporting to health authorities. As per the Sponsor's standard operating procedures,*

*prospective requests to deviate from the protocol, including requests to waive protocol eligibility criteria, are not allowed.*

### **9.3 SITE INSPECTIONS**

Site visits will be conducted by the Sponsor or an authorized representative for inspection of study data, patients' medical records, and eCRFs. The investigator will permit national and local health authorities, Sponsor monitors, representatives, and collaborators, and the IRBs/ECs to inspect facilities and records relevant to this study.

### **9.4 ADMINISTRATIVE STRUCTURE**

This study will be sponsored and managed by F. Hoffmann-La Roche Ltd.

Electronic data capture will be used for this study. An IxRS will be used to assign patient numbers. A central laboratory will be used for a subset of laboratory assessments as specified in Section 4.5.6; otherwise, local laboratories will be used. A central independent review facility will be used to collect PET-CT and CT scans, and the IRC will perform independent assessments of response for all patients enrolled in the study (separate IRC Charter will contain all details). Data from this study will be shared with an expert scientific committee that will provide scientific input for the benefit• risk assessment

### **9.5 PUBLICATION OF DATA AND PROTECTION OF TRADE SECRETS**

Regardless of the outcome of a study, the Sponsor is dedicated to openly providing information on the study to healthcare professionals and to the public, both at scientific congresses and in peer-reviewed journals. The Sponsor will comply with all requirements for publication of study results. For more information, refer to the Roche Global Policy on Sharing of Clinical *Study Information* at the following Website:

*[http://www.roche.com/roche\\_global\\_policy\\_on\\_sharing\\_of\\_clinical\\_study\\_information.pdf](http://www.roche.com/roche_global_policy_on_sharing_of_clinical_study_information.pdf)*

The results of this study may be published or presented at scientific congresses. For all clinical studies in patients involving an IMP for which a marketing authorization application has been filed or approved in any country, the Sponsor aims to submit a journal manuscript reporting primary clinical study results within 6 months after the availability of the respective clinical study report. In addition, for all clinical studies in patients involving an IMP for which a marketing authorization application has been filed or approved in any country, the Sponsor aims to publish results from analyses of additional endpoints and exploratory data that are clinically meaningful and statistically sound.

The investigator must agree to submit all manuscripts or abstracts to the Sponsor prior to submission for publication or presentation. This allows the Sponsor to protect

proprietary information and to provide comments based on information from other studies that may not yet be available to the investigator.

In accordance with standard editorial and ethical practice, the Sponsor will generally support publication of multicenter studies only in their entirety and not as individual center data. In this case, a coordinating investigator will be designated by mutual agreement.

Authorship will be determined by mutual agreement and in line with International Committee of Medical Journal Editors' authorship requirements. Any formal publication of the study in which contribution of Sponsor personnel exceeded that of conventional monitoring will be considered as a joint publication by the investigator and the appropriate Sponsor personnel.

Any inventions and resulting patents, improvements, and/or know-how originating from the use of data from this study will become and remain the exclusive and unburdened property of the Sponsor, except where agreed otherwise.

## **9.6            PROTOCOL AMENDMENTS**

Any protocol amendments will be prepared by the Sponsor. Protocol amendments will be submitted to the IRB/EC and to regulatory authorities in accordance with local regulatory requirements.

Approval must be obtained from the IRB/EC and regulatory authorities (as locally required) before implementation of any changes, except for changes necessary to eliminate an immediate hazard to patients or changes that involve logistical or administrative aspects only (e.g., change in Medical Monitor or contact information).

**Appendix 1**  
**Schedule of Activities for Patients with Follicular Lymphoma**  
**(Dose-Escalation and Expansion Phases)**

	Screening a		Induction (6 Cycles; 28-Day Cycles)								EOI	Maint. (24 Months)	EOM b	Post- Treatment FU Period (Q3M) d	Survival FU Period (Q3M) d
	D -28 to D -1	D -14 to D -1	Cycle 1 (± 1 d)				Cycle 2 (± 2 d)		Cycles 3-6 (± 2 d)		After Last Induction Dose c	Every 2 Months (± 1 wk)	35 Days After Last Dose		
			D1	D5	D8	D15	D1	D15	D1	D15		D1			
Informed consent e	x														
Demographic data	x														
Medical history	x														
ECOG Performance Status	x														
Vital signs f	x		x		x	x	x			x	x g	x	x		
Height	x														
Weight and body surface area	x														
12-lead ECG	x		x h	x h						x i	x	x h	x		
Complete physical examination j,k	x														
Targeted physical examination k,l			Cycles 2 and 4								x	x	x	x	
Ann Arbor, FLIPI, and FLIPI2	x														
B symptoms m	x														
β 2 microglobulin			x												
Hematology n		x	x o,p		x p	x p	x p	x	x p	x	x g	x	x		

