**Table 7 Post-Induction Treatment for the Expansion Phase**

Post-Induction Treatment	
Patients with FL	Maintenance treatment consisting of the following: 
 
• Obinutuzumab 1000 mg IV every 2 months for 24 months
 
• Idasanutlin for 6 months a
 

Patients with DLBCL	Consolidation treatment consisting of the following: 
 
• Rituximab 375 mg/m^2 IV every 2 months for 6 months
 
• Idasanutlin for 6 months a
 

DLBCL = diffuse large B-cell lymphoma; FL = follicular lymphoma; IV = intravenous.

a Dose and regimen to be determined by the Sponsor after review of all relevant data. The dose for maintenance/consolidation will not exceed the dose the patient received during induction.

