### ***Neutropenia and Febrile Neutropenia***

*In Study NP27872, a possible exposure-dependent neutropenia was shown, with AUC/cycle as a determinant for Grade 4 neutropenia within the first two cycles in the daily schedule.*

*Blood counts will be monitored closely throughout study treatment (see the schedules of activities in [Appendix 1](#) and [Appendix 2](#)); a Grade • 3 decrease in neutrophil levels should be followed until resolution (to Grade • 2 or baseline value) and additional measures considered as clinically indicated (see [Section 5.1.5](#)). Use of hematopoietic growth factors is encouraged during study treatment, particularly for patients who experience a first event of Grade • 3 neutropenia during the study treatment phase.*

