## Appendix 1 Schedule of Activities for Patients with Follicular Lymphoma (Dose-Escalation and Expansion) (cont.)

	Screening a		Induction (6 Cycles; 28-Day Cycles)								EOI	Maint. (24 Months)	EOM b	Post-Treatment FU Period (Q3M) d	Survival FU Period (Q3M) d
	D • 28 to D • 1	D • 14 to D • 1	Cycle 1 (± 1 d)				Cycle 2 (± 2 d)		Cycles 3•6 (± 2 d)		After Last Induction Dose c	Every 2 Months (± 1 wk)	35 Days After Last Dose		
			D1	D5	D8	D15	D1	D15	D1	D15		D1			
Serum chemistry q		x	x o, p		x p	x p	x p	x	x p	x	x g	x	x		
Coagulation (INR, aPTT [or PTT], and PT)		x													
Pregnancy test r		x									x g		x		
Hepatitis B and C testing s	x														
Quantitative IgA, IgG, IgM			x								x	x t	x	x u	
PK sample for obinutuzumab			x v												
PK sample for idasanutlin			x v												
Whole blood for MRD w			x p				x				x	x t	x		
Whole blood for lymphocyte immunophenotyping x			x p			x p	x p			x p	x	x t	x	x u	
Serum for MIC-1			x v	x v			x v,y			x v,z					
Optional peripheral blood sample for RCR aa			x	x											
Tumor tissue specimen (leftover tissue may be used for optional RCR specimen bb )	x bb		x cc												

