### Schedule of Activities for Patients with Follicular Lymphoma (Dose-Escalation and Expansion) (cont.)

- m Unexplained fever > 38°C, nightsweats, unexplained weight loss > 10% of body weight over 6 months.
- n Includes hemoglobin, hematocrit, platelet count, RBC count, WBC count, and percent or absolute WBC differential count (neutrophils, eosinophils, basophils, monocytes, lymphocytes, other cells).
- o Screening laboratory assessments may be used for Day 1 of Cycle 1 if performed within 72 hours prior to Day 1 of Cycle 1.
- p Perform hematology and chemistry tests within 72 hours prior to Day 1 of each cycle and within 24 hours prior to Days 8 and 15 of Cycle 1. Samples for exploratory biomarker research should be collected at the same time as hematology and chemistry samples.
- q Includes sodium, potassium, glucose, BUN or urea, creatinine, calculated creatinine clearance, calcium, total bilirubin, direct bilirubin, total protein, albumin, ALT, AST, alkaline phosphatase, amylase, lipase, LDH, and uric acid.
- r All women who are not postmenopausal (• 12 months of non-therapy-induced amenorrhea) or surgically sterile will have a serum pregnancy test at screening within 7 days prior to Day 1 of Cycle 1. Because of the suspected effect of idasanutlin on embryo-fetal development, monthly pregnancy testing is strongly recommended for women of childbearing potential ([CTFG 2014](#)).
- s Includes hepatitis B surface antigen, total hepatitis B core antibody, and hepatitis C virus antibody.
- t Perform at the same time as tumor assessments at 12, 18, and 24 months after initiation of induction treatment.
- u Perform every 3 months until recovery to either normal range or baseline level, disease progression, or the start of new anti-lymphoma treatment, whichever occurs first.
- v See [Appendix 3](#) and [Appendix 4](#) for detailed schedule.
- w Includes circulating lymphoma cells and/or cell-free circulating tumor DNA.
- x Includes B-cell counts (CD19), T-cell counts (CD3, CD4, and CD8), and NK-cell counts (CD16 and CD56).
- y Also on Day 5 of this cycle. See [Appendix 3](#) and [Appendix 4](#) for detailed schedule.
- z Cycle 4 Day 1 and Day 5. See [Appendix 3](#) and [Appendix 4](#) for detailed schedule.

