## Appendix 1 Schedule of Activities for Patients with Follicular Lymphoma (Dose-Escalation and Expansion) (cont.)

is lost to follow-up, or the patient withdraws consent. Every effort should be made to follow all serious adverse events considered to be related to any of the study treatment components or trial-related procedures until a final outcome can be reported.

ee The screening PET-CT scan must be performed within 35 days prior to Day 1 of Cycle 1.

ff Perform only for patients who have received at least two cycles of induction treatment.

gg If PET-CT scan is positive at EOI, perform at 12 months after initiation of induction treatment, within 14 days prior to treatment administration.

hh CT scan of the neck (if clinically indicated), chest, abdomen and pelvis. If contrast is medically contraindicated (e.g., patients with contrast allergy or impaired renal clearance), MRI scans of the chest, abdomen, and pelvis (and neck, if clinically indicated) and a non-contrast CT scan of the chest may be performed. Combined PET/CT scanners may be used to collect diagnostic CT scans but only according to the technical guidelines in the imaging manual. Screening CT scan must be performed within 35 days prior to Day 1 of Cycle 1.

ii Perform at 12, 18, and 24 months after initiation of induction treatment, within 14 days prior to treatment administration.

jj Perform only if not done within the previous 3 months.

kk Perform every 6 months.

ll Bone marrow biopsy and aspirate must be performed within approximately 3 months prior to Day 1 of Cycle 1.

mm For patients with bone marrow involvement at screening, a repeat assessment will be performed at EOI if there is radiologic evidence of a complete response, and during maintenance or at EOM if there is radiologic evidence of a complete response or if clinically indicated (e.g., if there is clinical suspicion of progressive disease in the bone marrow with no radiologic evidence of progression).

nn Refer to Section [4.3.2.3](#) and Section [4.3.2.5](#) for details on dosing and schedule.

oo Perform within 7 days prior to Day 1 of Cycle 3.

pp *Regimen will be defined based on available safety, tolerability, PK, and PD data.*

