### Schedule of Activities for Patients with DLBCL (cont.)

- c Consolidation treatment should start 8 weeks ( $\pm 1$  week) after Day 1 of the final cycle of induction and will continue until disease progression or unacceptable toxicity for up to 8 months.
- d Patients who complete consolidation treatment or discontinue consolidation treatment prematurely will undergo assessments at the EOC.
- e Patients who complete treatment or discontinue treatment for reasons other than disease progression will undergo assessments every 3 months during the post-treatment FU period, which will continue until disease progression, the start of new anti-lymphoma treatment, or the end of the study, whichever occurs first. The first post-treatment FU visit is 3 months after the EOI visit. Patients who experience disease progression will undergo limited assessments every 3 months during the survival FU period, which will continue until the end of the study. The end of the study is defined as the time when all enrolled patients with FL have completed or discontinued study treatment and all enrolled patients with DLBCL have been followed for at least 1 year after they have completed or discontinued study treatment.
- f Informed consent must be documented before any study-specific screening procedure is performed.
- g Vital signs include respiratory rate, pulse rate, body temperature, and systolic and diastolic blood pressures while the patient is in a seated position. For obinutuzumab infusions: For the first cycle and for patients who experience an infusion-related reaction, vital signs will be measured prior to the infusion, every 15 ( $\pm 5$ ) minutes for the first 90 minutes of the infusion, and then every 30 ( $\pm 10$ ) minutes until 1 hour after completion of the infusion. For the second and subsequent cycles, vital signs will be measured every 30 minutes during the infusion, except in patients who had experienced an infusion-related reaction during a prior infusion.
- h Perform only for patients who will not be receiving consolidation treatment.
- i Vital signs will be measured, a targeted physical examination will be performed, and hematology and serum chemistry will be assessed during consolidation every 2 weeks during the first month, every month until EOC. For rituximab infusions: Vital signs monitoring during infusion should be determined as per local label.

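### FL patients on maintenance idasanutlin have scheduled blood counts only every 2 months, while DLBCL patients on idasanutlin for the same 6 months are tested every 2 weeks and then monthly, and nothing in the plan reconciles the two

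*Combined protocol and SAP*

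**What the plan says.** - **Exposure.** Table 7 lists "Idasanutlin for 6 months" after induction for both FL and DLBCL expansion patients. Its footnote leaves dose and regimen to the sponsor and caps the dose at what the patient received in induction. FL patients from dose escalation get obinutuzumab alone in maintenance (Table 3).
- **FL schedule.** Appendix 1 has one maintenance column, headed "Every 2 Months (± 1 wk", Day 1. Hematology, serum chemistry, vital signs and targeted examination are each marked there, with no footnote adding assessments between visits. Footnote p ("Perform hematology and chemistry tests within 72 hours prior to Day 1 of each cycle") is attached to induction cells only. The maintenance idasanutlin cell carries footnote pp, "Regimen will be defined based on available safety, tolerability, PK, and PD data", which concerns the drug regimen and not the testing.
- **DLBCL schedule.** Appendix 2 footnote i states that "hematology and serum chemistry will be assessed during consolidation every 2 weeks during the first month, every month until EOC". It sets the same timing for vital signs and targeted examination.
- **General commitment.** Section 5.1.3.2 says "Blood counts will be monitored closely throughout study treatment" and refers to Appendices 1 and 2 for the timing.
- **Rules that need a count.** Table 20 withholds study treatment in maintenance for Grade 3 or 4 hematologic toxicity. Section 5.2.3 makes neutropenia and thrombocytopenia of Grade 3 or higher events of special interest, reportable within 24 hours.

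**The concern.** The same drug is given for the same 6 months in two arms, and one arm is tested far less often. The plan gives no reason. Its own statements do not suggest that FL needs less testing: Section 1.4 puts Grade 3 or higher hematologic toxicity at 3% to 14% for obinutuzumab and 1% to 4% for rituximab, and Section 3.3.3 expects less pronounced overlap of toxicities with rituximab. The FL laboratory grid matches the 2-monthly obinutuzumab dosing interval. An idasanutlin cell and footnote pp appear in that column, but nothing was added to the laboratory rows, so this looks like an omission.

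Two things are at stake. First, the withholding rule and the 24-hour reporting both depend on a cytopenia being found, and a silent one is found only by a count. Second, expansion data are summarized by histology (Section 6), so FL laboratory toxicity would be described from sparser testing than DLBCL laboratory toxicity.

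**Working it through.** The plan gives no figure of its own on this point, so the check is a count of scheduled draws.

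**Inputs.** FL interval of 2 months with a window of 1 week either side (Appendix 1). DLBCL at weeks 2 and 4, then monthly (Appendix 2 footnote i). Duration 6 months in both arms (Table 7). One month is taken as 30.4375 days, so 6 months = 182.6 days. A draw at the start of post-induction treatment is counted in both arms. Footnote i does not name that draw, and without it each DLBCL count below falls by one.

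| | FL | DLBCL |
|---|---|---|
| Draws before month 6 | months 0, 2, 4 = 3 | day 0, weeks 2 and 4, months 2, 3, 4, 5 = 7 |
| Including month 6 | 4 | 8 |
| Longest gap | 2 × 30.4375 = 60.9 days | 60.9 − 28 = 32.9 days |
| Longest FL gap with windows | 60.9 + 7 + 7 = 74.9 days | – |

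The difference is 7 − 3 = 4 draws (8 − 4 = 4 including month 6). For comparison, Appendix 1 schedules counts for Day 1 and Day 15 of Cycles 2 to 6 in induction.

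**Illustration of what the gap means.** Assume a cytopenia of duration d days whose onset is uniform over the 6 months, and ask how often a scheduled draw falls within it. The probability is the sum over gaps g of min(d, g), divided by 182.6. The FL gaps are 60.9 days three times. The DLBCL gaps are 14, 14, 32.9 and four of 30.4 days. For d = 14:

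- FL: 3 × 14 / 182.6 = 23%.
- DLBCL: 7 × 14 / 182.6 = 54%.

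| Duration (days) | FL | DLBCL |
|---|---|---|
| 7 | 11% | 27% |
| 14 | 23% | 54% |
| 21 | 34% | 73% |
| 28 | 46% | 92% |
| 42 | 69% | 100% |

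Durations and uniform onset are assumptions. Onset would in practice follow the dosing days, which are not yet defined. If courses were monthly (assumption), those at months 1, 3 and 5, half of six, would start without a scheduled count. If courses fell only on the 2-monthly visits, every course would have a pre-dose count, although nothing would be scheduled between visits.

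**Does another part of the plan fill the gap?** Section 5.1.3.2 sends the reader back to the appendices. The Appendix 1 note that assessments precede dosing sets the order on scheduled days and adds none. No other section sets more frequent FL maintenance counts.

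**The case against.** Several stronger readings are tempting, and the documents do not support them.

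- **That FL cytopenias simply go unseen.** Those present on a visit day are caught, symptomatic ones can surface through continual adverse event collection, and unscheduled tests are not barred. The problem is first detection of silent events between visits.
- **That after a cytopenia is found, the next count comes too late for the 42-day discontinuation limit in Table 20.** Known events are not left to the visit grid. Sections 5.1.1.3, 5.1.1.4 and 5.1.3.2 call for continued monitoring of neutropenia and thrombocytopenia, and Section 5.5.1 requires follow-up of every adverse event.
- **That a planned tolerability comparison between FL and DLBCL is biased.** None is planned. The amendment rationale added post-induction idasanutlin to explore benefit, and the arms receive different antibodies. Only the descriptive laboratory-based rates lose comparability.
- **That Appendix 1 footnote g, which omits the end-of-induction count for patients going on to maintenance, is a further gap.** That visit falls 6 to 8 weeks after Day 1 of the last cycle, and maintenance starts at 8 weeks (±1 week) with a pre-dose count. The omitted test is a near duplicate.
- **That this exposure stands out for having no DLT assessment.** The DLT window covers only the first cycle, or the first two in Regimen B, so later induction cycles lie outside it too. The post-induction dose is also capped at the induction dose.

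Two general points carry some weight. The regimen is undecided, so the sponsor may intend to set the testing with it; yet footnote pp mentions only the regimen. The internal monitoring committee reviews cumulative safety data, but it can review only what has been measured.

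Table 14 reports Grade 3 or higher thrombocytopenia of 44% and neutropenia of 27% in 34 patients on single-agent 5-day idasanutlin at 100 to 800 mg/day. Those patients came from the solid tumor study with the MBP formulation (Table 1). The rates show that the risk is not trivial. They are not estimates for FL responders who have completed induction.

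**Conclusion.** The inconsistency is real and should be resolved before any FL patient starts maintenance idasanutlin. Followed as written, Appendix 1 leaves first detection of a silent Grade 3 or 4 cytopenia to counts about 61 days apart (up to about 75), against about 33 for DLBCL, with 3 scheduled counts against 7. Table 20 withholding and 24-hour reporting may then not be triggered, and laboratory-detected toxicity in FL would be under-ascertained relative to DLBCL.

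The scope is limited to expansion-phase FL patients with a CR or PR, during the idasanutlin months of a 24-month maintenance period. CR at end of induction precedes this period and is untouched. The schedule counts rest on the 6-month duration in Table 7; Appendix 2 footnote c says up to 8 months for DLBCL consolidation, which is a separate discrepancy. The detection percentages are illustrative, and the practical size of the gap depends on the regimen still to be defined.

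**What to change.** When the post-induction idasanutlin regimen is set, and before FL maintenance idasanutlin begins, the sponsor should reconcile the Appendix 1 maintenance column with Appendix 2 footnote i and Section 5.1.3.2. One way is an Appendix 1 footnote on the hematology, chemistry, vital-sign and targeted-examination cells, stating how often these are done while an expansion-phase FL patient receives idasanutlin. The other is a written justification for testing FL less often than DLBCL. Footnote i is a model already in the plan; the final frequency is for the sponsor to decide.

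The cost is one footnote. If footnote i were adopted, it would add about 4 local-laboratory draws per patient over the 6 months, with the accompanying vital signs and targeted examinations, and no extra imaging. If the frequencies stay different, the study report should say so wherever post-induction laboratory toxicity is shown by histology.
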